5.3.2 MDS-UPDRS

5.3.2.1 Primary efficacy endpoint

Estimand:

The estimand of the primary analysis is the mean difference of the change from baseline in MDS-UPDRS I+II+III total score at Week 52 between treatment groups in the ITT population in a hypothetical setting where subjects do not start PD medication. MDS-UPDRS data collected after the intercurrent events, i.e., subjects start PD medication will be excluded in the primary analysis. Specifically, the estimand takes the following into consideration:

- A. Population: ITT population as defined in Section 5.1.2
- B. Variable: change from baseline to Week 52 in MDS-UPDRS score
- C. Intercurrent events: had PD medication not been made available to subjects prior to Week 52
- D. Population-level summary: difference in variable means between treatment conditions.

CONFIDENTIAL

The information contained herein may not be used, disclosed, or published without the written consent of Biogen MA Inc.

MMRM will be used as the primary analysis to analyze the change from baseline in MDS-UPDRS score. The model includes the fixed effects of treatment group, time (categorical), baseline PD subtype (categorical; PIGD vs TD vs indeterminate), prior use of PD medication (categorical), treatment group-by-time interaction, region (categorical), baseline MDS-UPDRS I+II+III total (continuous), baseline MDS-UPDRS I+II+III total by time interaction and baseline striatum SBR values (continuous), and baseline striatum SBR by time interaction. A random intercept and slope will be included in the model to model the random effects within subjects. If small sample size in subgroups of PD types causes lack of model convergence, the indeterminate group will be combined with the TD group. The Kenward-Roger approximation will be used to estimate the denominator degrees of freedom. Least square means (LSmeans) of each treatment group as well as treatment difference between BIIB054 groups and placebo will be displayed with 95% CI and p-value at Week 52. If the distribution of the outcome is highly skewed, p-value will be generated from the MMRM model based on ranked data. In the primary analysis, missing data are assumed to be missing at random (Rubin 1976), and MDS-UPDRS I+II+III score is impacted by PD medication.

The multiple comparison procedure-modelling (MCP-MOD) method will be used to assess the dose-response relationship while controlling for multiplicity (Pinheiro 2013). The dose-response parameter of interest for MCP-MOD are the least-squares means (LSmeans) at Week 52 for each treatment group from the MMRM model. The underlying models to be tested are specified in [Figure 4.1](#). P-value of dose response will be presented. Details of MCP-MOD procedure are specified in Appendix III.

A multiple comparison adjustment method will be applied to control the overall type I error at 0.05 in the study, due to the primary endpoint of change from baseline in MDS-UPDRS total score being analyzed at Week 52 and Week 72, and superiority against placebo is considered reached in the study if statistically significant result is achieved at either timepoint at the respective adjusted alpha-level. This will be applied to the p-value from the MCP-MOD model. Please refer to Section 6 “Interim Analyses” for more detail.

Nominal p-values for pair-wise comparison of each active group vs placebo will be reported, no additional multiple comparison adjustment will be applied.

Item 1.6 of features of dopamine dysregulation syndrome will be excluded to calculate all the scores.

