4 SAMPLE SIZE JUSTIFICATION

The sample size calculation is based on changes in MDS-UPDRS Part I + II + III total score at Week 52 and at Week 72 of treatment. Based on data from the Parkinson's Progression Markers Initiative study, the placebo subject's mean and standard deviation (SD) at Week 52 and Week 72 are assumed to be 8.0 (10.64) and 9.6 (13.7) respectively. Assuming a maximum of 55% reduction in the change from baseline in the active group with maximum response relative to placebo group, the mean (SD) for this active group will be 3.2 (10.64) and 3.84 (13.7) respectively at Week 52 and Week 72, and the responses for other active groups are assumed to be somewhere between 0 and the maximum response. The primary analysis will be based on the MCP-MOD method to detect a dose-response trend while controlling for multiplicity. Optimal contrasts will be constructed to detect potential dose-response trend under common dose-response curves (e.g., E_{max} , exponential, logistic, linear in log dose, and quadratic model, which are illustrated with parameters shown in [Figure 4.1](#) which will be used for both Week 52 and Week 72). The planned enrollment is 311 subjects total (24 subjects in Cohort A and 287 subjects in Cohort B, [4.1](#)). Actual enrollment is 357 subjects. In Cohort A, 29 subjects were randomized in a 1:1:1:1 ratio to each of the treatment groups, while in Cohort B 328 subjects were randomized in 2:1:2:2 ratio to the placebo, 250 mg, 1250 mg, and 3500 mg groups. Based on the actual enrollment, the estimated number of subjects by cohort and treatment groups are given in [Table 4.4.2](#) below. After accounting for dropout rate of 10% and 15% at Week 52 and Week 72, respectively, the estimated sample sizes are given in [Table](#) and [Table 1](#). With the updated sample size, the study will provide an average power of approximately 80% to detect the dose-response trend over 1 year of treatment, based on a 2-sided type I error of 0.05 and approximately 73% of power at the Week 72 analyses, based on a 2-sided type I error of 0.05. Overall, the sample size in the study will provide approximately 89% power, taking into consideration success at either Week 52 or Week 72. The final candidate models for the MCP-MOD are prespecified and described below.

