With an estimated sample size of 100 subjects dosed per arm in the 1250 mg and 3500 mg arms, the study has 80% probability of detecting AEs with a rate of 1.6% or greater in these 2 arms, and a 90% probability of detecting AEs occurring with a rate of 2.3% or greater.

Table 4.1: Estimated Sample Size Per Group (Planned)

	Treatment Group				Total
	Placebo	BIIB054 250 mg	BIIB054 1250 mg	BIIB054 3500 mg	
Cohort					
Cohort A	6	6	6	6	24
Cohort B	82	41	82	82	287
Total	88	47	88	88	311

Table 4.2: Estimated Sample Size Per Group Based on Actual Enrollment (Before Drop-Outs)

	Treatment Group				Total
	Placebo	BIIB054 250 mg	BIIB054 1250 mg	BIIB054 3500 mg	
Cohort					
Cohort A	8	7	7	7	29
Cohort B	93	47	94	94	328
Total	101	54	101	101	357

Table 4.3: Estimated Sample Size Per Group Based on Actual Enrollment (After Adjusting for 10% Drop-Out At Week 52)

	Treatment Group				Total
	Placebo	BIIB054 250 mg	BIIB054 1250 mg	BIIB054 3500 mg	
Cohort					
Cohort A	7	6	6	6	25
Cohort B	84	42	84	84	294
Total	91	48	90	90	319

[figure not shown]
Table 1: Estimated Sample Size Per Group Based on Actual Enrollment (After Adjusting for 15% Drop-Out At Week 72)

	Treatment Group				Total
	Placebo	BIIB054 250 mg	BIIB054 1250 mg	BIIB054 3500 mg	
Cohort					
Cohort A	7	6	6	6	25
Cohort B	79	40	80	80	279
Total	86	46	86	86	304

CONFIDENTIAL

The information contained herein may not be used, disclosed, or published without the written consent of Biogen MA Inc.

Figure 4.1: Candidate Models for Dose-Response

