5.3 Efficacy Endpoints

5.3.1 General Consideration

Clinical efficacy (clinical function) Assessments include Movement Disorder Society Sponsored Revision of the Unified Parkinson's Disease Rating Scale (MDS-UPDRS), [REDACTED]

[REDACTED]

[REDACTED] The questionnaire as well as the scoring algorithm for all these clinical assessments are described in Appendix I.

Unless otherwise noted, the analysis will be performed based on all the subjects in both Cohort A and B and the common visits. For numerical outcomes, the actual value and the change from baseline will be presented by treatment group and visit. For categorical outcome, the count and frequency will be summarized by treatment group and visit.

Analysis population

All clinical function endpoints will be evaluated in the ITT population as defined in Section 5.1.2. MDS-UPDRS [REDACTED] may also be analyzed in the per protocol population as defined in Section 5.1.2.

Baseline value

MDS-UPDRS, [REDACTED] are assessed at both screening visit and Day 1 visit. [REDACTED]

CONFIDENTIAL

The information contained herein may not be used, disclosed, or published without the written consent of Biogen MA Inc.

██████████. For all of them, the baseline values are defined as the latest data collected prior to or on the first dose date.

Visit windows for mapping clinical function endpoint

Assessments from all scheduled visits, EOT visit and EOS visit, and unscheduled visits will be mapped to an appropriate analysis visit using a windowing scheme (Appendix II).

Handling missingness of itemed question score

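### Efficacy models pool two cohorts randomised at different ratios with no cohort term, leaving a small, design-built imbalance in the 250 mg versus placebo contrast

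*SAP*

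**What the plan says.** SAP Section 4 states the two allocation schemes. The earlier cohort was allocated equally across the four arms: "In Cohort A, 29 subjects were randomized in a 1:1:1:1 ratio to each of the treatment groups". The later cohort gave the low dose half the weight of the other arms: "in Cohort B 328 subjects were randomized in 2:1:2:2 ratio to the placebo, 250 mg, 1250 mg, and 3500 mg groups". Section 3.1.1 adds that the cohorts ran in sequence. Cohort B could start only after all of Cohort A had completed Week 12 and the IDMC had reviewed the data.

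For efficacy, Section 5.3.1 pools them: unless otherwise noted, "the analysis will be performed based on all the subjects in both Cohort A and B and the common visits".

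Section 5.3.2.1 specifies the primary MMRM: "The model includes the fixed effects of treatment group, time (categorical), baseline PD subtype". The list goes on to earlier use of PD drugs, region, the interaction of treatment with time, and the baseline total score and baseline striatum SBR, each also crossed with time. Cohort is absent. It is also absent from the EP-RPS ANCOVA (Section 5.3.2.4), the MMRM for other clinical endpoints (Section 5.3.3) and the imaging MMRM (Section 5.5.5). The Week 72 primary analysis in the extension-period SAP (Section 4.3.2) refers back to the Year 1 SAP for its model. The visible text plans no by-cohort or Cohort B-only efficacy analysis.

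**The concern.** When two randomised cohorts with different allocation ratios are pooled, treatment is independent of cohort only within cohort. The chance of 250 mg is 1/4 in Cohort A and 1/7 in Cohort B, so the pooled 250 mg arm holds proportionately more Cohort A subjects than placebo does. This follows from the design. It is not a chance imbalance and does not shrink as the trial grows. If the cohorts progress differently for reasons the covariates do not capture, a fraction of that difference is read as a 250 mg effect. It then passes into the nominal pairwise p-value and, through the LSmeans, into MCP-MOD.

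The model adjusts for continuous versions of both Cohort B stratification factors but not for the one factor on which the allocation probability itself changes. A cohort difference is conceivable, because enrolment was sequential and calendar time may bring changes in assessment conditions. The documents do not report one.

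**Working it through.** **1. Reproduce Table 4.2.** Cohort A: 29/4 = 7.25 per arm. Cohort B: 328 × 2/7 = 93.7 and 328 × 1/7 = 46.9. The table gives 8/7/7/7 and 93/47/94/94 (placebo, 250, 1250, 3500 mg), totals 101/54/101/101 = 357. It agrees up to rounding.

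**2. Cohort A share by arm.**

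| Sizes used | Placebo | 250 mg | 1250 and 3500 mg | 250 mg minus placebo |
|---|---|---|---|---|
| Table 4.2 | 8/101 = 7.9% | 7/54 = 13.0% | 7/101 = 6.9% | +5.0 points |
| Planned (Table 4.1) | 6/88 = 6.8% | 6/47 = 12.8% | 6/88 = 6.8% | +6.0 points |
| Unrounded ratios | 7.25/100.96 = 7.2% | 7.25/54.11 = 13.4% | 7.2% | +6.2 points |
| After 10% dropout (Table 4.3) | 7/91 = 7.7% | 6/48 = 12.5% | 6/90 = 6.7% | +4.8 points |

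Placebo, 1250 mg and 3500 mg are allocated equally in both cohorts, so the ratios create no imbalance among them. The 1.0-point gap in Table 4.2 arises only because the 29th Cohort A subject is counted under placebo.

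**3. Bias in 250 mg minus placebo at Week 52.** Bias = (share in 250 mg − share in placebo) × G, where G is the cohort difference in mean change left after covariate adjustment. G is not in the documents and is an assumption here. With Table 4.3 sizes the multiplier is 0.125 − 0.077 = 0.048. With the Section 4 SD, SE = 10.64 × √(1/91 + 1/48) = 1.898. With z = bias/SE, the type I error of the nominal 0.05 pairwise test is 1 − Φ(1.96 − z) + Φ(−1.96 − z). The MCP-MOD column is simulated from the seven candidate models in Appendix III with optimal contrasts, at the 0.04 allocated to Week 52.

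| Assumed G (points) | Bias (points) | Bias/SE | Pairwise 250 mg type I error (nominal 0.05) | MCP-MOD type I error (nominal 0.04) |
|---|---|---|---|---|
| 2 | 0.10 | 0.05 | 0.050 | 0.040 |
| 5 | 0.24 | 0.13 | 0.052 | 0.041 |
| 8 | 0.38 | 0.20 | 0.055 | 0.042 |
| 10.64 (one SD) | 0.51 | 0.27 | 0.058 | 0.043 |

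With unrounded ratios and no dropout the multiplier is 0.062, so G = 8 gives 0.062 × 8 = 0.50 points.

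**4. Why MCP-MOD hardly moves.** With 91/48/90/90 subjects, the absolute weight on 250 mg in the optimal contrasts is 0.12 to 0.25, against 0.37 to 0.76 on placebo and 0.53 to 0.86 on 3500 mg. At G = 8 the bias of any contrast is at most 0.14 SE.

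**5. Price of adjusting.** From a one-time-point linear model with treatment only, then treatment plus cohort, the SE of 250 mg versus placebo goes from 1.898 to 1.901 at Week 52. At Week 72 (86 and 46 subjects, SD 13.7) it goes from 2.503 to 2.507. Both rises are about 0.2%. The SEs for the other doses do not change to three significant figures.

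**6. Is a cohort main effect enough?** Change from baseline starts at zero, so a difference in progression grows with time, and a term that is constant over visits cannot fit it at Week 52. In a check with a random intercept and slope, assumed variances, assumed 8-weekly visits plus Week 52, and a difference growing linearly to 8 points, a main effect alone cut the Week 52 bias only from 0.385 to 0.23–0.26. About 60 to 70% stayed. The exact fraction depends on the assumed variances.

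**The case against.** The strongest reply is that this is too small to matter. Cohort A is 29 of 357 subjects, and about one twentieth of a cohort difference reaches one pairwise contrast, whose p-value is nominal by Section 5.3.2.1. What counts is the difference left after adjustment for region, PD subtype, prior PD medication, baseline total score and baseline SBR. The last two are the Cohort B stratification factors, so describing stratification for Cohort B only adds nothing to the concern. An 8-point residual difference would equal the whole placebo change assumed in Section 4. All of this stands, and it sets the weight of the point.

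Two stronger inferences are tempting. A reader might conclude that the 250 mg comparison is in substance a comparison of cohorts, or that 250 mg anchors the dose-response test and the bias carries through to it. The 5-point difference in mix and the low contrast weight on 250 mg do not support that. A reader might also take the 1.0-point difference in Table 4.2 as bias for 1250 mg and 3500 mg. It is a rounding effect in a table of estimated sizes, and at planned sizes it is zero.

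What the reply leaves untouched is that the dependence of allocation on cohort is known in advance, nothing else in the visible text addresses it, and adjusting for it costs almost nothing.

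**Conclusion.** The point holds as a minor refinement. The pooled models omit the factor by which allocation to 250 mg differs, so that contrast carries an imbalance of about 5 percentage points in cohort mix. If the residual cohort difference at Week 52 is 2 to 8 points, the bias is about 0.1 to 0.4 points (0.05 to 0.20 SE), or 0.5 points at the upper end with unrounded ratios. MCP-MOD type I error at 0.04 becomes at most about 0.042 over that range.

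These figures rest on an assumed cohort difference, on estimated arm sizes, and on a single-visit calculation with the planning SD and no other covariates. If the cohorts do not differ after adjustment, there is no bias. The documents do not support reading this as a threat to the primary conclusion.

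**What to change.** Prespecify cohort (A/B) and cohort-by-time as fixed effects in the primary MMRM, the MDS-UPDRS sub-part MMRMs, the imaging MMRM and the Week 72 model. Add cohort as a fixed effect to the EP-RPS ANCOVA.

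Do not make cohort-by-time conditional on how the fitted model behaves, because that puts a data-dependent choice into the primary analysis. If the interaction is judged too heavy for the primary model, keep that model and prespecify either the cohort-adjusted model or a Cohort B-only analysis as a sensitivity analysis.

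The cost is one degree of freedom for cohort plus one for each additional visit, and an SE for 250 mg versus placebo about 0.2% larger in the one-time-point calculation. No new data are needed.

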5.2.2 Demographics and Baseline Characteristics

Demographic data, including age (in years), age category (40-50, 51-60, 61-70, 71-80 years), gender, race, ethnicity, height, weight, body mass index (BMI), country (region) and year of education at baseline will be summarized by treatment groups and overall.

Baseline PD history will be summarized by treatment groups and overall, using descriptive statistics. Time since onset of PD symptoms (in years), time since PD diagnosis (in years), subtype of PD (PIGD, TD or indeterminate), side predominately affected at disease onset, symptoms presented at PD diagnosis and immediate family with a history of Parkinson's Disease will be summarized. MDS-UPDRS total and subtotal scores, PIGD, TD, and LE subscore, Hoehn and Yahr stage, [REDACTED] will be summarized. DaT/SPECT imaging outcomes, [REDACTED] outcomes will also be summarized. Baseline MDS-UPDRS score is defined as the Day 1 visit, if Day 1 visit score is not available, screening visit will be used. Baseline PD history data will be listed.

Number (%) of subjects with any PD treatment history will be summarized by treatment groups and overall. Total duration of previous therapies and reason for stopping therapies will be summarized. Number (%) of subjects who had taken MAO-B inhibitors, Dopamine Agonist, Levodopa and other PD medications will be displayed by treatment groups and overall. A listing of PD treatment history will be generated.

Medical history will be coded using the Medical Dictionary for Regulatory Activities (MedDRA). The number (%) of subjects with history (including both ongoing and not ongoing medical conditions) will be summarized by system organ class and preferred term, and by preferred term only. A listing of medical history will be generated.

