4.3.2 Primary efficacy endpoint analysis

The estimand of the primary analysis for MDS-UPDRS Part I+II+III total score at Week 72 is the mean difference of the change from baseline at Week 72 between treatment groups in the ITT population regardless of whether start of PD medication had occurred or not. Specifically, the estimand takes the following into consideration:

- A. Population: ITT population as defined in Section 4.1.1;
- B. Variable: change from baseline to Week 72 in the MDS-UPDRS Part I+II+III total score;
- C. Intercurrent events: regardless of whether start of PD medication had occurred or not;
- D. Population-level summary: difference in variable means between each early start group and delayed start group

Change from baseline in the MDS-UPDRS Part I+II+III total score at Week 72 will be analyzed using an MMRM model for all the visits in the placebo-controlled and DBE period.

Data after subjects start PD medication will be included in the primary analyses.

For details on the model to be used please refer back to the Year 1 SAP, for the analyses of MDS-UPDRS including data after PD medication. Adjusted means for each treatment group,

CONFIDENTIAL

The information contained herein may not be used, disclosed, or published without the written consent of Biogen MA Inc.

	Statistical Analysis Plan Dose Blinded Extension Period	V2.0
---	--	-------------

pairwise adjusted differences for the comparisons, 95% confidence intervals for the differences will be presented at each visit, and p-values will be presented for the key visits of week 24, 52, and 72. Dose-response testing will be done using the adjusted mean with the pre-specified MCP-MOD procedure with pre-specified candidate models (refer to Year 1 SAP Sample Size Consideration section). If the distribution of the outcome is highly skewed, p-value will be generated from the MMRM model based on the rank data. Missing data are assumed to be missing at random behind the MMRM model.

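### The primary models adjust for one of two available pre-dose MDS-UPDRS scores; adding the screening score is a cheap, conditional gain in precision

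*SAP*

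**What the plan says.** Year 1 SAP, section 5.3.1, says of MDS-UPDRS and other scales that they "are assessed at both screening visit and Day 1 visit", and that "the baseline values are defined as the latest data collected prior to or on the first dose date". Section 5.2.2 gives the same order of preference: "Baseline MDS-UPDRS score is defined as the Day 1 visit, if Day 1 visit score is not available, screening visit will be used". Only one pre-dose value per subject therefore reaches the model, and where Day 1 exists that value is Day 1.

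The primary MMRM in section 5.3.2.1 contains "baseline MDS-UPDRS I+II+III total (continuous), baseline MDS-UPDRS I+II+III total by time interaction", together with baseline striatum SBR and its interaction with time, PD subtype, prior PD medication and region. It has no term for the screening score. Section 5.3.2.2 reuses the model for Parts I, II and III, replacing the baseline total with the one matching sub-part baseline. For Week 72, the extension SAP (section 4.3.2) states: "For details on the model to be used please refer back to the Year 1 SAP". The pointer is to the version that includes data after PD medication. Section 5.3.2.3 of the Year 1 SAP changes the covariance structure and the data included for that version, but not the baseline covariates.

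The sample size section (section 4) assumes that the placebo mean changes (SD) "are assumed to be 8.0 (10.64) and 9.6 (13.7) respectively" and mentions no gain from covariates.

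**The concern.** The outcome is change from Day 1, so any visit-to-visit rating error on Day 1 is carried into the change score at every later visit. Adjusting for Day 1 alone recovers only part of this, because a single score cannot separate true severity from that day's error. Two scores taken before treatment can do so in part. The screening score precedes randomisation, so using it as a covariate does not bias the comparison of arms.

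At stake is some residual variance in the Week 52 and Week 72 dose-response tests and in the Part I, II and III comparisons. Stated power is about 80% and 73% at two-sided 0.05, while section 6 starts testing at 0.04 and 0.01. A small gain from data already collected is therefore worth having.

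**Working it through.** **Inputs from the SAP.** SD of change 10.64 (Week 52) and 13.7 (Week 72); placebo change 8.0 and 9.6; "Assuming a maximum of 55% reduction in the change from baseline in the active group with maximum response"; evaluable subjects per arm (placebo/250/1250/3500 mg) 91/48/90/90 = 319 and 86/46/86/86 = 304; the seven candidate shapes in Appendix III.

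**Assumed, because the SAP does not give them.** r = correlation of screening with Day 1; ρ = correlation of the outcome-visit score with Day 1; kρ = correlation of the outcome-visit score with screening.

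**Step 1: reproduce the stated power.** A 55% reduction gives maximum effects of 0.55 × 8.0 = 4.4 and 0.55 × 9.6 = 5.28. MCP-Mod was simulated with optimal contrasts for the seven shapes and a critical value of about 2.24 at two-sided 0.05, and power was averaged over the shapes. The result is 81.7% at Week 52 and 73.9% at Week 72 (simulation error about 0.1 point), against the stated 80% and 73%. The printed active means of 3.2 and 3.84 imply effects of 4.8 and 5.76, a 60% reduction. These give 87.8% and 81.0% and do not reproduce the stated figures. That mismatch is a separate matter; the 55% effect is used below.

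**Step 2: variance ratio.** Once Day 1 is a covariate, analysing the change or the follow-up score leaves the same residual variance, proportional to 1 − ρ². With both pre-dose scores:

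R² = ρ²(1 + k² − 2rk)/(1 − r²), and ratio = (1 − R²)/(1 − ρ²).

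If both scores predict equally well (k = 1), the ratio is [1 − 2ρ²/(1 + r)]/(1 − ρ²).

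- r = 0.90, ρ = 0.6: (1 − 0.72/1.90)/0.64 = 0.970; 1/0.970 = 1.031, about 3% more effective subjects.
- r = 0.85, ρ = 0.7: (1 − 0.98/1.85)/0.51 = 0.922; 1/0.922 = 1.084, about 8% more.

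**Step 3: power after adding screening.** The stated SD is taken as the Day 1-adjusted SD and multiplied by the square root of the ratio; the test is two-sided at 0.05.

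| r | ρ | k | Ratio | Effective n | Week 52 | Week 72 |
|---|---|---|---|---|---|---|
| Day 1 only | – | – | 1.000 | – | 81.7% | 73.9% |
| 0.90 | 0.6 | 1 | 0.970 | +3.1% | 82.9% | 75.2% |
| 0.85 | 0.6 | 1 | 0.954 | +4.8% | 83.5% | 75.9% |
| 0.90 | 0.7 | 1 | 0.949 | +5.3% | 83.7% | 76.1% |
| 0.85 | 0.7 | 1 | 0.922 | +8.4% | 84.7% | 77.4% |
| 0.90 | 0.6 | 0.95 | 0.993 | +0.7% | 82.0% | 74.2% |
| 0.85 | 0.7 | 0.95 | 0.965 | +3.6% | 83.0% | 75.4% |
| any | any | r | 1.000 | 0 | 81.7% | 73.9% |

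With k = 1, the gains run from 82.9 − 81.7 = 1.2 to 84.7 − 81.7 = 3.0 points at Week 52, and from 75.2 − 73.9 = 1.3 to 77.4 − 73.9 = 3.5 points at Week 72. In the last row, screening carries nothing beyond Day 1 and the gain is zero. The most favourable corner examined (r = 0.80, ρ = 0.75, k = 1) gives a ratio of 0.857 and power of 87.2% and 80.3%.

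**Step 4: two variations.** At the initial testing levels, the case r = 0.90, ρ = 0.6, k = 1 moves Week 52 power from about 79% to 80% (0.04) and Week 72 power from about 51% to 53% (0.01). If the stated SDs are instead unadjusted SDs of change, and scores have equal variance at both visits, Day 1 adjustment already multiplies the variance by (1 + ρ)/2 = 0.80 at ρ = 0.6. Power is then 89.3% and 83.0% with Day 1 alone, and 90.2% and 84.1% with screening added (r = 0.90).

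**The case against.** The strongest reply is that the plan contains no error here. Change from the last pre-dose value, adjusted for that value and its interaction with time, is conventional, valid and consistently specified. That stands, and the point is made only as an efficiency improvement.

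A reader might infer that power is certainly lost at both timepoints. The documents do not support this: no correlation between screening and Day 1, or between baseline and outcome, is given, and the gain shrinks to zero when screening adds nothing.

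A reader might also try to extract the rating noise from the plan's own SDs. Setting 2s² + c·52² = 10.64² and 2s² + c·72² = 13.7² gives c = (187.69 − 113.21)/(5184 − 2704) = 0.0300, 2s² = 113.21 − 81.21 = 32.0 and s = 4.0. This is two equations in two unknowns, so it fits any such pair and tests nothing. If slope variance grew with t rather than t², then c = 74.48/20 = 3.724, 52c = 193.6 exceeds 113.21, and the noise variance is negative. Had the Week 72 SD been 14.7, s would be about 0.7. The figure is a product of the assumed growth curve, and no estimate here relies on it.

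It is also fair that the calculation treats one visit with complete data. It ignores the other covariates and, at Week 52, the exclusion of data after PD medication starts. Extra subjects on 319 is therefore not a literal description of that analysis. These points limit the precision of the estimate rather than its direction. The larger model also adds some risk of non-convergence, for which section 5.3.2.1 already plans.

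**Conclusion.** The point holds as a modest, conditional efficiency gain. Two pre-dose scores are collected and one enters the primary models at Week 52 and, by reference, at Week 72. Adding the other is worth about 3% to 8% in effective sample size, or about 1 to 3.5 power points at each timepoint. This assumes r between 0.85 and 0.90, ρ between 0.6 and 0.7, and two scores that predict the outcome equally well. If screening predicts slightly less well (k = 0.95), the gain over the same range is 0.7% to 3.6% in effective sample size, and it may be near zero.

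Two further readings should be resisted. The stated 80% and 73% are not overstated on this account, since they claim no covariate gain and reproduce without one. Nor is the screening score thrown away altogether, because it serves as baseline when Day 1 is missing. The direction of the effect is secure; its size is not.

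**What to change.** Before unblinding at each timepoint, keep change from Day 1 as the endpoint and add the screening MDS-UPDRS I+II+III total and its interaction with time to the Week 52 and Week 72 primary MMRMs. In the Part I, II and III models, add the matching sub-part screening score and its interaction with time. Where a screening score is missing, substitute the Day 1 score and include a missing indicator, so that no subject is dropped. If the model does not converge, drop the screening-by-time interaction first. Blinded pooled data can supply the screening/Day 1 correlation, to show whether the gain is worth having.

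The cost is SAP wording, a few degrees of freedom and a slightly larger model; no new data are needed and the estimand does not change. Section 5.3.5 refers to the Week 52 database lock in the past tense. If a timepoint has already been unblinded, its primary model should stay as written and the version with screening should be reported as supplementary.
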